#### 5.9.1 Study treatment premature discontinuation

The decision to prematurely discontinue study treatment may be made by the study participant, the investigator/delegate, or the sponsor personnel.

The investigator/delegate has the option of prematurely discontinuing study treatment for a given study participant in response to an AE, a diagnostic or therapeutic procedure, a laboratory abnormality, or for administrative reasons. If study treatment is interrupted by the study participant for any reason, she/he must inform the investigator/delegate as soon as possible. Study treatment dose interruptions must be recorded in the eCRF.

The investigator/delegate must permanently discontinue study treatment for a given study participant if, on balance, he/she believes that continued administration would be contrary to the best interests of the study participant.

Study-specific criteria for permanent discontinuation of study treatment are described in Sections 5.9.1.1 to 5.9.1.4.

The main reason for permanent discontinuation of study treatment (e.g., due to pre-specified study treatment discontinuation criteria, an AE, lack of efficacy, study termination) must be documented in the eCRF.

A study participant who prematurely discontinues study treatment is not considered as withdrawn from the study.

The study participant who prematurely discontinues study treatment or who is permanently discontinued from study treatment will be asked to return for an EOT visit within 1 to 5 days of last intake of study treatment and thereafter to attend follow-up visits as defined in the schedule of activities [Table 1, Section 7.2].

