Estimand	Target Population	Endpoint	Strategy for addressing intercurrent events	Population- level summary
Supplementary Estimand #2	Adult study participants with BED according to DSM-5, having at least 3 BE days per	Change from baseline to Week 12 in the number of BE days per week	Hypothetical, i.e., endpoint data after intercurrent event are not used.	Mean change from baseline to Week 12 for each treatment group.

Treatment effect

completing expressed as 12 weeks of difference of treatment LSMean without use of changes from other baseline to medication Week 12 (ACT-539313 minus placebo; from mixed model)

week at baseline,

Intercurrent events are premature discontinuation of treatment and use of other, forbidden, medication for BE.

BE = binge eating; BED = binge eating disorder; DSM-5 = Diagnostic and Statistical Manual of Mental Disorders (5th edition); LSMeans = Least Squares Means.

In the choice of intercurrent events it was considered that, in symptomatic settings, it is not the usual practice to continue to assess effectiveness in subjects after they have stopped taking the assigned treatment [O'Neill 2012]. Also, if an alternative (or additional) drug is started, this could influence the outcome for a subject [O'Neill 2012]. Therefore, two types of intercurrent events were considered: premature discontinuation of double-blind treatment (ACT-539313 or placebo) and use of other forbidden medication for BE.

Excluding measurements obtained after an intercurrent event will lead to a hypothetical strategy estimand (ICH E9[R1]). A hypothetical strategy is related to the scenario in which the intercurrent events would not occur (i.e., all subjects completing the 12 weeks of assigned treatment without using forbidden BE medication), which is a reasonable approach for this proof-of-concept study.

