6.3 Analysis of exploratory efficacy variables

The following efficacy endpoints will be summarized using descriptive statistics:

- Change from baseline up to Week 12 (EOT) in the number of BE episodes per week^a.
- Absence of BE episodes ('Yes'^b/'No') during the last 4 weeks of the treatment period^c.
- Change from baseline to Week 12 (EOT) in the total score of the YBOCS-BE.
- Change from baseline to Week 12 (EOT) in the subscales scores (i.e., compulsive/obsessive, restraint, control) of the YBOCS-BE.
- Change from baseline to Week 6 (Visit 6) and to Week 12 (EOT) in the HAMD-17 total score.
- Change from baseline to Week 6 (Visit 6) and to Week 12 (EOT) in the HAMD-17 subitems 10 and 11.
- Change from baseline to Week 6 (Visit 6) and to Week 12 (EOT) in the HAMD-17 Maier-Philipp Subscale (MPS) score.
- Change from baseline to Week 12 (EOT) in EDE-Q7 global score and 3 subscales scores (i.e., dietary restraint, shape/weight overvaluation, body dissatisfaction).
- CGI-C score at Week 12 (EOT).
- PGI-C score at Week 12 (EOT).
- Change from baseline to Week 12 (EOT) in the CGI-S score.
- Change from baseline to Week 12 (EOT) in the PGI-S score.
- Change from baseline to Week 12 (EOT) in body weight.
- Change from baseline to Week 12 (EOT) in HbA1c^d.
- Improvement^e according to CGI-C score at Week 12 (EOT).

^a 'Number of BE episodes per week' is defined as the number of BE episodes in the applicable 14-day time interval divided by the total number of diary days, times 7.

^b 'Yes' is defined as BE episodes equal to 0.

^c 'Last 4 weeks of the treatment period' are defined as study days 57–84 [see Section 11.7].

^d Glycated hemoglobin.

^e Improvement according to CGI-C score is defined as CGI-C at Week 12 equal to "Much Improved" or "Very much improved". If CGI-C at Week 12 is missing, the study participant will be assumed to not have improved.

The above variables related to change from baseline will be summarized along with their observed values.

The YBOCS-BE is an interviewer-administered assessment developed to measure the severity of obsessive-compulsive symptoms in subjects with a diagnosis of obsessive-compulsive disorder modified to measure the BE thoughts and behaviors. The YBOCS-BE

ACT-539313		Statistical Analysis Plan
ID-082A201	Confidential	for Clinical Study Report
1 April 2022, page 30/60	Confidential	Version 3
		Doc No D-22.100

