• The change from baseline to Week 6 (Visit 6) and to Week 12 (EOT) in the HAMD-17 total score, subitems 10 and 11, and MPS score, with a covariate for the time points limited to Week 6 (Visit 6) and Week 12 (EOT).

Absence of BE episodes will be analyzed using a logistic regression model with a factor for treatment group, sex and BMI category, and a covariate for the baseline number of BE episodes per week. For study participants who discontinued treatment prematurely, the outcome will be set to 'No absence'.

The CGI-C and PGI-C scores at Week 12 (EOT) will be compared between treatment groups using the Kruskal-Wallis test. Missing assessments at Week 12 will be imputed using last on-treatment observation carried forward.

The change from baseline to Week 12 (EOT) in the CGI-S score, PGI-S score, body weight and HbA1c will be analyzed using an ANCOVA model with a factor for treatment group and a covariate for baseline score. Missing assessments for CGI-S and PGI-S score at Week 12 will be imputed using last on-treatment observation carried forward.

The improvement according to CGI-C score at Week 12 (EOT) will be analyzed using a logistic regression model with a factor for treatment group.

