11.6 Missing data patterns

A monotone missing data pattern is defined as follows: given a dataset with variables Y1, Y2, ..., Yt (in that order) and Vj is missing for a particular subject, then all subsequent variables Vk, k > j, are missing for that subject. In addition, given the same dataset and Vj is observed for a particular subject, then all previous variables Vk, k < j, are also observed for that subject. Monotone missing data patterns are typically encountered when a subject prematurely withdraws from a study and is expected to be more likely seen than non-monotone missing data patterns.

In the examples below, an 'X' indicates that the variable is observed in the corresponding group and a '.' means that the variable is missing.

Subject	Y1	Y2	¥3
1	Х	Х	Х
2	Х	Х	
3	Х		

Example of monotone missing data patterns:

When missing data are non-monotone, data can also be missing at intermediate visits (i.e., missing at a given visit, but observed again at the next visit). Non-monotone missing data patterns are commonly turned into monotone missing data patterns using MI (based on MCMC), which are then subsequently analyzed using MI methods based on monotone missing data.

Example of non-monotone missing data patterns:

Subject	Y1	Y2	Y3
1	X	Х	Х
2		Х	Х
3			Х
4		Х	
5	Х		Х

11.7 Time window definitions for calculating efficacy and safety endpoints collected through diary

BE episodes (efficacy) and daytime sleepiness (safety; measured using the SSS) are the endpoints collected daily through a diary. The BE diary will be filled in from the start of the screening period until EOT while the SSS will only be filled in during the first 2 weeks of treatment (from randomization [Visit 2] to Visit 4).

Table 6 defines the time windows used to calculate number of BE episodes/days per week.

Table 6Time windows (in days) to calculate weekly averages for the efficacy
endpoints BE episodes/days collected daily through the diary

Weeks	Study day (14-day window)
1–2	1–14
3–4	15–28
5–6	29–42
7–8	43–56
9–10	57–70
11–12	71–84

For the calculation of absence of BE episodes ('Yes'/'No') during the last 4 weeks of the treatment period, a minimum of 4 out of 7 diary entries are required for days 57–63, 64–70, 71–77 and 78–84, otherwise the outcome will be set to 'No absence'. Absence of BE episodes ('Yes') is defined as BE episodes equal to 0.

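### The remission and CGI-C improvement endpoints have no rule for participants who start a forbidden BE medication, although the SAP names this as an intercurrent event

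*SAP*

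**What the plan says.** SAP 6.1.2 gives the intercurrent events as "premature discontinuation of double-blind treatment (ACT-539313 or placebo) and use of other forbidden medication for BE". Its reason for including the second is that an alternative or added drug could affect a participant's outcome. SAP Table 3 applies a hypothetical strategy, in which data after the event are not used, to BE days per week (primary estimand and supplementary estimand #2) and to BE episodes per week (supplementary estimand #1).

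For absence of BE episodes in the last four weeks, SAP 6.3 and Protocol 9.2.4.2 have the same rule: "For study participants who discontinued treatment prematurely, the outcome will be set to 'No absence". SAP 11.7 requires at least 4 of 7 diary entries in each of the four weeks, and continues: "otherwise the outcome will be set to 'No absence'. Absence of BE episodes ('Yes') is defined as BE episodes equal to 0".

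For CGI-C improvement, the footnote in SAP 6.3 has one failure rule: "If CGI-C at Week 12 is missing, the study participant will be assumed to not have improved". The analysis is a logistic regression with treatment as the only factor.

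Protocol 6.2.2 forbids medication for BE during the study. On stopping study treatment, Protocol 5.9.1 says: "Study-specific criteria for permanent discontinuation of study treatment are described in Sections 5.9.1.1 to 5.9.1.4". Those sections cover pregnancy, contraception, liver aminotransferases and COVID-19.

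**The concern.** The plan recognises that another BE drug can change the outcome and sets aside the BE-day and BE-episode data that follow it. For the two responder endpoints the same period is scored as observed. A binge-free month or a good global rating achieved on lisdexamfetamine or topiramate, both listed in SAP Table 9, is then credited to the arm the participant was randomized to.

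The discontinuation rule does not close this gap. Use of forbidden medication is not a listed criterion for stopping study treatment, so a participant can take such a drug and still complete treatment. The investigator may stop treatment, but nothing listed requires it for this reason.

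At stake is the meaning of two exploratory results in the study report. Both are tested at the two-sided 5% level, and four-week remission is an endpoint in the protocol synopsis.

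**Working it through.** The plan states no expected rate, sample size or power for either responder endpoint, so there is no figure of its own to reproduce on this point. The power figures in Protocol Table 6 concern the primary endpoint; they reproduce (78.2%, 90.8% and 97.0% by normal approximation with 60 per arm, against 78%, 91% and 97% stated) but do not bear on it.

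**1. Rules side by side**

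| Endpoint | Early stop of study treatment | Forbidden BE medication | Other failure rule |
|---|---|---|---|
| BE days, BE episodes per week (SAP 6.1.2, Table 3) | Later data not used | Later data not used | Not applicable |
| Absence of BE episodes, days 57–84 (SAP 6.3, 11.7) | 'No absence' | None | Too few diary entries |
| CGI-C improvement (SAP 6.3) | None explicit | None | Missing Week 12 rating |

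The example code in SAP 14.6 and 14.7 has no medication rule. The Table 9 list is called on only in SAP 6.1.7, for the primary endpoint. SAP 12.3 and 12.4 add no clarification.

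**2. One participant through the plan**

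Take a participant who starts topiramate on study day 43, stays on study treatment, completes the diary, has no BE episodes on days 57–84 and is rated 'Much Improved' on day 85.

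- BE days and BE episodes: the windows for days 1–42 are used; those for days 43–84 are not.
- Remission: no discontinuation, full diary, zero episodes, hence 'Yes'.
- CGI-C improvement: a rating exists in the Week 12 window (days 78–92, SAP Table 7), hence improved.

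If the SAP 6.1.2 exclusion were read across to remission, days 57–84 would have no usable entries and the result would be 'No absence'. SAP 6.3 does not say to do this, so two programmers could score this participant differently.

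**3. CGI-C after early discontinuation**

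Protocol Table 1 puts the early end-of-treatment visit 1 to 5 days after the last dose. A last dose on day 73 allows a visit on day 73 + 5 = 78, the first day of the Week 12 window. A participant who stops early from about that day on can have a Week 12 rating that counts as observed.

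**4. Size**

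Input: about 120 participants, 1:1 (Protocol 6.1.3), so 60 per arm.

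- One participant: 1/60 = 1.7 percentage points.
- Three participants: 3/60 = 5.0 points.

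The number of users is not given. As an illustration only, assume remission of 9/60 (15%) on placebo and 21/60 (35%) on ACT-539313, and let *k* participants in one arm be added as successes on a Table 9 drug. The formulas are OR = [a/(60−a)] / [b/(60−b)] and SE(ln OR) = √(1/a + 1/(60−a) + 1/b + 1/(60−b)), with an unadjusted Wald p-value. The planned model also adjusts for sex, BMI category and baseline.

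| Added successes | ACT-539313 | Placebo | OR | p |
|---|---|---|---|---|
| None | 21 | 9 | 3.05 | 0.014 |
| 1 on placebo | 21 | 10 | 2.69 | 0.024 |
| 2 on placebo | 21 | 11 | 2.40 | 0.042 |
| 3 on placebo | 21 | 12 | 2.15 | 0.069 |
| 3 on ACT-539313 | 24 | 9 | 3.78 | 0.003 |

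Scoring these participants as non-responders returns the first row. A few cases can matter, and in either direction.

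**The case against.** Several points on the other side are sound.

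- *No stated rule is broken.* This stands. A reader might infer that the SAP violates its own estimand. It does not: the intercurrent events are defined for the primary objective, and no estimand is defined for these two endpoints. The defect is a gap and an inconsistency between endpoints in one report.
- *Other exploratory endpoints lack a rule too.* Also true of YBOCS-BE, HAMD-17, EDE-Q7, CGI-S and PGI-S. The responder endpoints stand out because the remission rule already codes one of the two events as failure and is silent on the other.
- *Non-responder coding does not reproduce the primary estimand.* Correct. It is a composite strategy and the primary estimand is hypothetical. The remission endpoint already differs in this way for discontinuers, so the strategy should be named and not presented as alignment.
- *The cut-off is blunt.* Someone binge-free to day 83 who starts a Table 9 drug on day 84 becomes a failure. That is the price of a simple pre-specified rule.
- *The event is restricted and visible.* Forbidden medication is a deviation category summarised by arm (SAP 5.2), concomitant therapies are tabulated, and urine drug screens run through the end-of-treatment visit. This would reveal cases but does not change how they are scored. The per-protocol set may remove some, but SAP 6.1.7 commits only the primary analysis to it, SAP Table 2 makes its efficacy use conditional on a size difference above 10%, and the deviation document that sets exclusions is not part of the documents.
- *The consequence is limited.* This stands: the endpoints are exploratory and described as descriptive, without Type I error control.

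**Conclusion.** The gap is real. As written, the plan counts a participant who stays on study treatment and does well on another BE drug as a success of the assigned arm on both responder endpoints. CGI-C improvement is the looser of the two, because it has no explicit rule for early discontinuation either.

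Each such participant moves an arm's rate by about 1.7 points, assuming 60 per arm. The number of cases may be zero. The p-values above rest on assumed remission rates and an assumed 20-point difference.

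A reader might infer that the gap will shrink the treatment effect because placebo participants would add medication more often. The documents give no frequency of forbidden-medication use by arm, so the direction is unknown; cases on ACT-539313 would inflate the effect. Nor does the gap touch the primary test, its power or the sample size. It merits a short SAP correction, in proportion to exploratory endpoints.

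**What to change.** Before unblinding, amend SAP 6.3 and 11.7 as follows.

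- **Remission:** set 'No absence' for anyone who starts a Table 9 medication on or before study day 84, next to the existing discontinuation rule.
- **CGI-C improvement:** set 'not improved' for anyone who started a Table 9 medication, or prematurely discontinued study treatment, before the Week 12 rating.
- **CGI-C and PGI-C scores:** treat ratings after the first Table 9 drug as missing and carry forward the last on-treatment rating before it.
- **Strategy:** state that the responder endpoints use a composite (non-responder) strategy, which differs from the hypothetical primary estimand.

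The cost is a few sentences and a derivation flag that the primary analysis already needs. Responder rates become slightly lower. If the sponsor prefers another strategy, stating it before unblinding would also close the gap. The change concerns analysis only and alters no rule on treatment or its discontinuation.

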# 7.2.4.3 Clinical Global Impression of Severity Scale

The CGI-S is a 1-item, 7-point scale that requires the investigator to rate the severity of the study participant's illness at the time of assessment, relative to the clinician's experience with patients who have the same diagnosis.

After a clinical evaluation, the CGI-S form can be completed in less than a minute by an experienced rater. In practice, the CGI-S captures clinical impressions that transcend mere symptom checklists. It ranges between "Normal, not at all ill" and "Among the most extremely ill patients". The CGI-S will be administered on a touchscreen device on site, at Visit 1 (Screening), Visit 2 (Randomization), Visit 5 (Week 4), Visit 7 (Week 8), and EOT (Week 12).

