#### 7.2.4.5 Patient Global Impression of Severity scale

The PGI-S is a question concerning the overall severity of symptoms and impact that the study participant may have experienced due to his/her BE episodes over the 7 days preceding the PGI-S completion.

ACT-539313		Doc No D-21.148
Binge Eating Disorder		
Protocol ID-082A201	Confidential	
Final Version 3		
4 May 2021, page 67/140		

It ranges between "No binge eating" and "Very severe". It is a self-administered questionnaire completed on a touchscreen device on site at Visit 2 (Randomization), Visit 5 (Week 4), Visit 7 (Week 8), and EOT (Week 12).

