# 9.2.4.1 Variable definitions

- Changes from baseline up to Weeks 11–12 in the number of BE episodes per week based on diary data, defined based on the 2-week intervals defined for the primary endpoint. The number of BE episodes per week is defined as the number of BE episodes in the applicable 14-day time interval divided by the total number of diary days, times 7.
- Absence of BE episodes during the last 4 weeks of the treatment period, defined as no BE episodes during study days 57–84. A minimum of 4 out of 7 diary entries are required for days 57–63, 64–70,71-77 and 78–84, otherwise the outcome will be set to 'No absence'.
- Change from baseline to Week 12 in EDE-Q7 global score, defined as the difference of EDE-Q7 global score at Week 12 and at Baseline. Variables for the EDE-Q7 subscales are change from Baseline to Week 12 in EDE-Q7 dietary restraint subscale score, change from Baseline to Week 12 in EDE-Q7 shape/weight overvaluation subscale score and change from Baseline to Week 12 in EDE-Q7 body dissatisfaction subscale scores.

- CGI-C score at Week 12. Missing assessments at Week 12 will be imputed using last on-treatment observation carried forward. Study participants with no on-treatment assessment will have a missing value. Additionally, improvement according to CGI-C is defined as CGI-C at Week 12 equal to "Much Improved" or "Very Much Improved". If CGI-C at Week 12 is missing, the study participant will be assumed to not have improved.
- PGI-C score at Week 12. Missing assessments at Week 12 will be imputed using last on-treatment observation carried forward. Study participants with no on-treatment assessment will have a missing value. Additionally, improvement according to PGI-C is defined as PGI-C at Week 12 equal to "Much Improved" or "Very Much Improved". If PGI-C at Week 12 is missing, study participant will be assumed to not have improved.
- Change from baseline to Week 12 in the CGI-S score, defined as the difference of CGI-S score at Week 12 and at Baseline. Missing assessments at Week 12 will be imputed using last on-treatment observation carried forward.
- Change from baseline to Week 12 in the PGI-S score, defined as the difference of PGI-S score at Week 12 and at Baseline. Missing assessments at Week 12 will be imputed using last on-treatment observation carried forward.

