presents three subscales: compulsive/obsessive (Items #1, 2, 3, 6, 7 and 8), restraint (Items #4 and 9), and control (Items #5 and 10).

The HAMD-17 is an indicator of depression and anxiety. The HAMD-17 consists of 17 items, with most items providing a score that ranges between 'Absent' and 'Almost all the time'. The MPS sub-score combines items 1 (depressed mood), 2 (guilt), 7 (work and activities), 8 (psychomotor retardation), 9 (psychomotor agitation), and 10 (anxiety, psychic).

EDE-Q7 is a self-reported questionnaire containing 7 of the 28 questions from the EDE-Q about eating behaviors (Items #1, 3, 4, 22, 23, 25 and 26). The EDE-Q7 presents three subscales: dietary restraint (Items #1, 3 and 4), shape/weight overvaluation (Items #22 and 23), and body dissatisfaction (Items #25 and 26).

The CGI-C is a 1-item, 7-point scale that ranges from "Very much improved" to "Very much worse".

The PGI-C is a 1-item, 7-point scale that ranges from "Very much improved" to "Very much worse".

The CGI-S is a 1-item, 7-point scale that ranges from "Normal, not at all ill" to "Among the most extremely ill patients".

The PGI-S is a question concerning the overall severity of symptoms and impact that the study participant may have experienced due to his/her BE episodes over the 7 days preceding the PGI-S completion. It ranges from "No binge eating" to "Severe".

The exploratory efficacy endpoints will be tested at two-sided 5% significance level. No further Type I error control is applied; hence, these analyses are to be considered descriptive.

The MMRM [Section 6.1.3], will be fitted for:

- The change from baseline to Week 12 (EOT) in the number of BE episodes per week, with a covariate for the baseline number of BE episodes (rather than the number of BE days) per week.
- The change from baseline to Week 12 (EOT) in EDE-Q7 global score and 3 subscales, with a covariate for the time points limited to Week 4 (Visit 5), Week 8 (Visit 7), and Week 12 (EOT).
- The change from baseline to Week 12 (EOT) in the total score of the YBOCS-BE and in the subscales scores (i.e., compulsive/obsessive, restraint, control), with a covariate for the time points limited to Week 4 (Visit 5), Week 8 (Visit 7) and Week 12 (EOT).

ACT-539313		Statistical Analysis Plan
ID-082A201	Confidential	for Clinical Study Report
1 April 2022, page 31/60	Confidential	Version 3
		Doc No D-22.100

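### CGI-S and PGI-S change at Week 12 is analysed by LOCF and a single-visit ANCOVA, although scales on the same Week 4/8/12 schedule get the MMRM; LOCF can bias the treatment difference in either direction

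*SAP*

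**What the plan says.** For CGI-S and PGI-S, SAP 6.3 says that change from baseline to Week 12 "will be analyzed using an ANCOVA model with a factor for treatment group and a covariate for baseline score". On missing scores it says: "Missing assessments for CGI-S and PGI-S score at Week 12 will be imputed using last on-treatment observation carried forward" (LOCF). Protocol 9.2.4.1 has the same rule ("Missing assessments at Week 12 will be imputed using last on-treatment observation carried forward"), and Protocol 9.2.4.2 has the same ANCOVA, so the two documents agree.

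Protocol 7.2.4.3 schedules CGI-S after randomization at "Visit 5 (Week 4), Visit 7 (Week 8), and EOT"; PGI-S (7.2.4.5), YBOCS-BE (7.2.4.2) and EDE-Q7 (7.2.4.7) follow the same visits. SAP 6.3 fits the MMRM of Section 6.1.3 to "The change from baseline to Week 12 (EOT) in EDE-Q7 global score and 3 subscales", and likewise to the YBOCS-BE total and subscales, with time points Weeks 4, 8 and 12. HAMD-17, which has only two post-baseline time points in its model, also gets the MMRM.

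SAP 6.3 tests the exploratory endpoints at the two-sided 5% level without further Type I error control and calls them descriptive.

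**The concern.** Four scales with one visit schedule are analysed in two ways, and neither document says why. Scoring on a short ordinal scale does not explain it, because the ANCOVA is also a linear model on the scores.

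LOCF sets a discontinuer's Week 12 value to an earlier one, possibly from Week 4, and treats it as observed. If scores are still improving, each arm's improvement is understated in proportion to its dropout. The treatment difference then moves when dropout differs by arm. It also shrinks under equal dropout if the effect is still growing.

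Changing profiles and missing data are both foreseeable. Protocol 4.3 says that the time an OX1R antagonist needs to act is unclear. Protocol 9.4 contemplates up to 20% missing Week 11–12 data. SAP 14.4 and 14.5 report 9 discontinuations from site closure, which is 9/120 = 7.5% of the planned sample. In the primary sensitivity analyses those participants are imputed under missing at random (MAR); here an early score could be carried forward for them.

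At stake are the clinician and patient ratings of global severity, not the primary result.

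**Working it through.** **1. The passages side by side**

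| Scale | Post-baseline visits | SAP Table 7 windows (days) | Week 12 analysis |
|---|---|---|---|
| CGI-S, PGI-S | Weeks 4, 8, 12 | 22–36, 50–64, 78–92 | LOCF; ANCOVA on treatment and baseline |
| YBOCS-BE, EDE-Q7 | Weeks 4, 8, 12 | 22–36, 50–64, 78–92 | MMRM (MAR), also with sex and BMI category |

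**2. The plan's own figures.** None is given for CGI-S or PGI-S. The primary-endpoint sample size reproduces: per arm, 2 × (1.96 + 1.282)² / 0.6² = 58.4, rounded up to 59, or 118 in total, as in Protocol Table 5. That calculation is not in question. It supplies 60 per arm and the figure of up to 20% missing, which is not split by arm.

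**3. Hand calculation (all inputs assumed).** Mean changes at Weeks 4/8/12 are −1.0/−1.5/−1.9 on active and −0.8/−1.1/−1.3 on placebo, so the visit differences are −0.2/−0.4/−0.6. Dropout is completely random; half the dropouts carry Week 4 forward and half carry Week 8. The LOCF mean in an arm is the sum over visits of (share whose last value is at that visit) × (mean at that visit).

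- 20% in each arm: 0.80(−0.6) + 0.10(−0.2) + 0.10(−0.4) = −0.54. Attenuation is 0.06/0.60 = 10%.
- 30% active, 15% placebo: active 0.70(−1.9) + 0.15(−1.0) + 0.15(−1.5) = −1.705; placebo 0.85(−1.3) + 0.075(−0.8) + 0.075(−1.1) = −1.2475. The difference is −0.46 (0.1425/0.60 = 24% attenuation).
- 10% active, 30% placebo: active 0.90(−1.9) + 0.05(−1.0) + 0.05(−1.5) = −1.835; placebo 0.70(−1.3) + 0.15(−0.8) + 0.15(−1.1) = −1.195. The difference is −0.64, so the benefit is overstated by 0.04.

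A simulation with these means (SD 1.1, correlation 0.6, 60 per arm, random or value-dependent dropout) gave −0.54 to −0.55 in the first case (8–10% attenuation) and −0.43 to −0.45 in the second (25–28%). Standard errors were 0.20–0.22 for LOCF and 0.21–0.23 for the MAR model.

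**4. Independent simulation in SD units** (true Week 12 effect −0.6 or 0, correlation 0.6, 60 per arm, 1,500 replicates, 48 runs). Participants with no post-baseline value were either excluded or given their baseline value. A positive bias understates benefit when the true effect is −0.6. Rows show random dropout with improving means.

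| Dropout, active/placebo | Effect | LOCF bias, excluded to baseline carried |
|---|---|---|
| 20% / 20% | −0.6, growing | +0.041 to +0.087 |
| 30% / 10% | −0.6, growing | +0.134 to +0.302 |
| 10% / 30% | −0.6, growing | −0.050 to −0.138 |
| 30% / 10% | none | +0.072 to +0.181 |
| 10% / 30% | none | −0.082 to −0.183 |

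The first row is 0.041/0.60 = 7% to 0.087/0.60 = 14.5% attenuation. Over all 48 runs LOCF bias ran from −0.26 to +0.34. The MMRM's was at most 0.008 in absolute value (Monte Carlo standard error about 0.004). LOCF bias was near zero in special cases, for example equal dropout with no effect.

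**5. Two gaps in the carry-forward rule.** The choice between excluding participants and carrying baseline roughly doubles the bias above, yet the documents do not make it for CGI-S and PGI-S. Protocol 9.2.4.1 sets participants without an on-treatment value to missing only for CGI-C and PGI-C. Second, Protocol Table 1 places a premature EOT visit 1 to 5 days after the last dose, with both scales collected. SAP 11.2 ends the treatment period for early discontinuers at the treatment end date, so whether that score is on-treatment is unclear.

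**The case against.** These endpoints are exploratory and descriptive, and the rule is prespecified identically in both documents. It also follows a convention: CGI-C and PGI-C use the same LOCF. All of that stands, and it limits the weight of the point. It does not explain why two change-from-baseline severity scales are separated from YBOCS-BE and EDE-Q7.

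The size rests on assumptions. Means, SD, correlation and dropout by arm are all assumed, and the larger figures need unequal dropout. Phase 1 had no discontinuations for adverse events, although dose-related somnolence, absent on placebo, makes unequal dropout conceivable. At equal 20% dropout the first simulation's bias is only about a quarter of the standard error (0.055/0.21). The MMRM looks unbiased partly by construction, because every simulated dropout mechanism was MAR or completely random. Premature-EOT scores were not modelled; if they count as on-treatment, the value carried is the status at discontinuation and the bias would differ. These objections stand, so the figures are illustrative.

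A reader might also infer that LOCF contradicts the trial's hypothetical estimand strategy. The documents do not support this. Protocol Table 4 and SAP Table 3 define estimands for the primary objective only, covering BE days and BE episodes. Other exploratory endpoints depart from that strategy openly: discontinuers are counted as not free of BE episodes, and a missing CGI-C counts as not improved.

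Nor does body weight share the weakness. It has the same ANCOVA but no LOCF rule, so how its missing values are handled is a separate question.

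**Conclusion.** The inconsistency is real and unexplained. LOCF can bias the Week 12 CGI-S and PGI-S differences in either direction when dropout differs by arm, and can attenuate a growing effect when dropout is equal. It would go too far to say that it will bias them whenever participants discontinue: the direction and size depend on dropout and trajectory, which the documents do not give, and the bias vanishes in some cases.

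Under the assumed inputs, attenuation is about 7 to 14% at 20% dropout per arm. With a 30%/10% split, random dropout and a growing effect it is 0.13 to 0.30 SD on a true effect of 0.6 SD. These figures ignore premature-EOT scores, and the MMRM's advantage holds only under MAR. The primary conclusion is unaffected. The change is still worth making, because the SAP already has the method and uses it on the same visits.

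**What to change.** In SAP 6.3, move CGI-S and PGI-S from the ANCOVA paragraph to the MMRM list, using the Section 6.1.3 model limited to Weeks 4, 8 and 12 with the scale's own baseline, as for YBOCS-BE and EDE-Q7. The code in SAP 14.1 can be reused.

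In the same place, state how premature-EOT assessments are assigned, including whether a score taken after the last dose enters the model. Table 7 has no CGI-S or PGI-S window for days 2–21, 37–49 or 65–77. That is 20 + 13 + 13 = 46 of the 91 days from day 2 to day 92, so an MMRM restricted to the three windows could discard early-EOT scores that LOCF might have used.

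Keep LOCF/ANCOVA as a secondary display, and say what it does when no post-baseline on-treatment score exists. List the change in SAP 12.1.

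The costs are a departure from Protocol 9.2.4.1 and 9.2.4.2, reliance on MAR, possible loss of out-of-window early-EOT scores, and a windowing rule to write. On the simulated standard errors, little precision is lost. CGI-C and PGI-C would stay on LOCF; they are compared by Kruskal-Wallis test, so this model does not transfer to them directly.
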